3.2 Randomization

A total of 20 healthy subjects will be enrolled and randomly assigned to group 1 or group 2 in a 1:1 ratio. Subjects who discontinue the study after randomization for non-safety related reasons may be replaced to ensure that the number of evaluable subjects in each group is not less than 8.

3.3 Hypothesis Testing

No formal statistical hypothesis testing will be conducted for this study.

3.4 Interim Analysis

There will be no interim analysis conducted.

3.5 Sample Size

The sample size for this study is not based upon formal statistical consideration. The sample size is considered adequate to characterize the PK of bexagliflozin, to assess potential drug-drug interactions, and to provide safety and tolerability data on bexagliflozin when administered with exenatide.

3.6 Schedule of Assessments and Study Procedures

Table 1. Schedule of Events

Study activity	Screening	Period 1					Period 2				
	D -21 to -1	D 0	D1 pre-dose	D1 post-dose	D 2	D3	D7	D8 pre-dose	D8 post-dose	D 9	D10
Medical history and ICF	X										
Screening for I/E criteria	X	X					X				
Physical exam ¹	X	X				X	X				X
Demographics	X										
Randomization		X									
Admission and discharge		X				X	X				X
Vital signs ²	X	X	X	X	X	X	X	X	X	X	X
ECG ³	X	X	X	X			X	X	X		X
Urinalysis ⁴	X	X				X	X				X
Blood draw for clinical lab tests ⁵	X	X				X	X				X
Blood sample for PK ⁶			X	X	X	X		X	X	X	X
Urine collection ⁷		X	X	X	X	X	X	X	X	X	X
Pregnancy Test	X	X					X				
Adverse event and concomitant medication		X	X	X	X	X	X	X	X	X	X
Study termination											X

Abbreviations: D = day; ECG = electrocardiogram; I/E = inclusion/exclusion; PD = pharmacodynamic; PK = pharmacokinetic.

- Weight and height will be recorded as part of the physical examination. Height will be recorded once at screening only. A complete physical exam (PE) will be performed at screening and day 10 prior to discharge. A partial PE will be performed on days 0, 3 and 7.
- Vital signs include: pulse, body temperature, respiratory rate, systolic and diastolic blood pressure. Vital signs will be recorded at screening, on days 0, 1 (predose, 4 h postdose), 3 (48 h postdose), 7, 8 (predose, 4 h postdose), and 10 (48 h postdose), and when clinically indicated.
- 12-lead ECG will be conducted after 10 min resting. ECG data will be recorded at screening, on days 0, 1 (predose, 4 h postdose), 7, 8 (predose, 4 h postdose), and 10 (48 h postdose), and when clinically indicated.
- Urine samples will be collected at screening, on days 0, 7 and prior to discharge in each period. If urine is dipstick positive for leukocyte esterase or nitrites, sample is to be sent for microscopic evaluation and culture. Urine drug screen will be performed on screening visit and on day 7. If drug screening is conducted more than 5 days prior to dosing, screening shall be repeated.
- Blood sample at the designated visits (screening, on days 0, 3, 7 and 10 for clinical chemistry and hematology parameters are listed in [Table 2](#). Blood will be drawn after 10 h of fasting prior to breakfast (i.e. only water is allowed, no caloric intake).
- Plasma samples for PK profile of bexagliflozin will be collected at pre-dose and at 0.5, 1, 2, 3, 4, 5, 6, 8, 10, 12, 16, 24, 36, and 48 h post-dose.
- Urine for urinary glucose (PD) and creatinine will be collected at pre-dose (h -12 to 0), and at post-dose at 0 to 12 h, 12 to 24 h, 24 to 36 h, and 36 to 48 h.

4. DATA AND ANALYTICAL QUALITY ASSURANCE

The overall quality assurance (QA) procedures for the study data, statistical programming and analyses are described in Everest's Standard Operating Procedures (SOPs). Detailed data management (DM) procedures are documented in the Data Management Plan, Data Validation Check Specifications, and Data Review Plan. Detailed statistical and programming quality control (QC) and QA procedures are documented in the Statistical Analysis and Programming QC/QA Plan.

The study endpoints and analytic approaches are both prospectively defined and documented in the protocol and in this SAP. The SAP will be finalized, and protocol violations will be identified and decisions for inclusion and exclusion of subjects from the PK and PD Populations will be made prior to the database lock and data analysis.

5. ANALYSIS POPULATIONS

Three subject populations will be evaluated during this study and are defined as follows:

5.1 Safety Population

The Safety Population will include all randomized subjects who receive at least one dose of the drug. Subjects will be analyzed according to the treatment received.

5.2 Pharmacokinetic Population

The PK Population will include all randomized subjects who receive study drug and who have sufficient plasma bexagliflozin measurements to derive at least one PK parameter following dosing. The PK Population will be used to summarize the PK parameters. Subjects will be analyzed according to the treatment received.

5.3 Pharmacodynamic Population

The PD Population will include all randomized subjects who receive study drug and have had 0-12 hr and 12 to 24 hr urine collection from which to calculate 24-hour UGE following dosing. The PD Population will be used to summarize the PD parameters. Subjects will be analyzed according to the treatment received.

6. SPECIFICATION OF ENDPOINTS AND VARIABLES

6.1 Demographic and Baseline Characteristics

Demographic variables consist of the following:

- Age in years (continuous) derived as the integer value of (informed consent date – date of birth + 1)/365.25
- Sex
- Race
- Ethnicity

Baseline characteristics consist of the following:

- Body mass index (BMI)

- Weight (kg)
- Height (cm)
- Vital signs
 - systolic blood pressure (SBP, mmHg)
 - diastolic blood pressure (DBP, mmHg)
 - oral temperature (°C)
 - pulse (beats per minute)
 - respiration rate
- Electrocardiogram (ECG) parameters
 - RR interval (msec)
 - PR interval (msec)
 - QRS duration (msec)
 - QT interval (msec)
 - QTcF interval (msec)
- Medical history and baseline conditions
- Clinical laboratory tests
- Prior and concomitant medication
- Physical examination

6.1.1 Study Day and Visit Window Definitions

Table 2. Time Windows for Safety Assessments

Time Windows for Safety Assessments			
Scheduled Visit Number	Visit (label)	Time Interval (day)	Target Time Point (day)
1	Screening	-21 to -1	-21 to -1
2	Day 0	0	0
3	Day 1	1	1
4	Day 2	2	2
5	Day 3	3-5	3
6	Day 7	7	7
7	Day 8	8	8
8	Day 9	9	9
9	Day 10	10-12	10

Data obtained during unscheduled visits will be allocated to the scheduled visit corresponding to the visit window they fall in as specified in Section 6.1.1. Safety data obtained during unscheduled time points will be allocated to the scheduled time point corresponding to the time window in which they fall. Data will be analyzed based on the nominal visits and nominal time points. If the data from the nominal visit or time point is missing, data from unscheduled visits for the same nominal visit or time point will be used. If multiple unscheduled assessments fall in the same visit window or time point, the non-missing assessment closest to target time point will be selected for analysis.

6.2 Pharmacokinetics/Pharmacodynamics

Pharmacokinetic/pharmacodynamic analysis will be performed on the PK and PD Populations respectively. Plasma samples will be analyzed for bexagliflozin concentrations using a validated method.

Blood samples for PK analysis will be collected in each period at pre-dose and at 0.5, 1, 2, 3, 4, 5, 6, 8, 10, 12, 16, 24, 36, and 48 h post dose.

Urine samples for PD analysis will be collected in 12 hr intervals.

Urine collection in 12 h batches will be performed at pre-dose (-12 to 0 h), and post-dose at 0 to 12 h, 12 to 24 h, 24 to 36 h, and 36 to 48 h.

6.3 Safety

Safety analysis will be performed on the Safety Population.

The safety profile of bexagliflozin will be assessed through the recording, reporting, and analyzing of adverse events, clinical evaluations, and laboratory tests.

Safety variables include the following:

1. Adverse events
2. Clinical laboratory measurements – serum chemistry, hematology, and urinalysis
3. Urine drug screen
4. Vital signs
5. ECG
6. Physical examination
7. Pregnancy test
8. Concomitant medications/treatments

6.3.1 Study Day and Visit Window Definitions

Refer to section 6.1.1 for details.

6.3.2 Extent of Exposure to Study Medication

Subjects who gave consent to participate in the study will be randomly assigned to 1 of the 2 groups. Subjects in each group will be randomly assigned to receive 1 of 2 treatment regimens in a crossover fashion with 2 treatment periods separated by a washout period of at least 7 days. Refer to Table 1 under Section 3.6.

In order to observe the maximal potential effect of exenatide on the absorption rate of bexagliflozin, bexagliflozin will be administered orally 30 min after subcutaneous exenatide injection, at 10 µg bid (the highest dose approved for use in the United States), meanwhile, the highest dose used (10 µg bid exenatide

injection in the United States) or intended to be used (20 mg bexagliflozin tablets) clinically will be selected.

6.3.3 Adverse Events (AEs)

Adverse events will be collected and coded using version 20.0 (or newer) of MedDRA. Analysis of adverse events will be carried out on the Safety Population. All adverse events will be included in the individual subject data listings. Only treatment emergent adverse events (TEAEs) will be tabulated in summary tables. The incidence of TEAEs will be presented by treatment. If the AE(s) onset date-time or date occurs after the first dose up until right before the second dose, the AE(s) will be assigned to the first treatment. If the AE(s) onset date-time or date occurs after the second dose, the AE(s) will be assigned to the second treatment.

All adverse events will be assessed by the investigator(s) with respect to severity, relationship to study drug and seriousness.

6.3.3.1 Treatment-Emergent AE (TEAE)

An adverse event is considered treatment-emergent if it occurs after bexagliflozin and/or exenatide administration and if the date of onset is on or after the date of first dose of study medication, or worsens during the treatment period (intensity/severity grades worsen).

6.3.3.2 Serious Adverse Events (SAE)

AEs will be categorized as serious or non-serious using the definition specified in Section 6.9 of the study protocol.

6.3.3.3 Immediately Reportable AE (IRAE)

An IRAE is any serious adverse event or any adverse event that necessitates discontinuation of the study drug.

6.3.3.4 Adverse Events Counting Rules

1. A subject with more than one different AE in a particular system organ class (SOC) will be counted only once in the total of subjects experiencing adverse events in that particular SOC.
2. A subject having experienced the same event (AE preferred term) more than once during the study will be counted only once in the number of subjects with that event.
3. A subject having experienced the same event (AE preferred term) more than once during the study with a different severity or seriousness, it will be counted only once with the worst grade and seriousness respectively.
4. A subject having experienced the same event (AE preferred term) more than once during the study with a different causal relationship to the study drug, it will be counted only once by considering the most-related documented degree of relationship.

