8.4.1 Adverse Events

All AEs will be coded to system organ class (SOC), and preferred term (PT), using the latest Medical Dictionary for Regulatory Activities coding dictionary (version to be specified in the clinical study report). All reported AEs will be listed, but only TEAEs will be summarized.

The incidence of all TEAEs will be summarized by treatment. In the summary tables, subjects may be counted under multiple SOCs and PTs, but for each SOC and PT, subjects are only counted once. If a subject has the same AE on multiple occasions, the highest severity (severe > moderate > mild) or drug relationship (definite > probable > possible > not likely related > unrelated) recorded for the event will be presented. If severity is missing, subjects will be included as missing (for severity). If drug relationship is missing, subjects will be included in related tables (e.g., considered related). Summary tables will be organized by SOC, then PT.

The following summaries will be presented for TEAEs:

- Overall Summary of TEAEs by Treatment
- Incidence of TEAEs by Treatment, System Organ Class, and Preferred Term
- Incidence of Treatment Emergent Serious Adverse Events by Treatment, System Organ Class, and Preferred Term

Subjects who prematurely discontinued due to TEAEs and subjects with serious TEAEs will be listed.

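### SAP 6.3.3.4 counts a repeated adverse event once per study; in this crossover, with tables by treatment, the scope should be once per treatment

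*SAP*

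**What the plan says.** SAP 6.3.3.4 has four counting rules. Rule 1 counts a subject once per system organ class and names no time span. Rules 2 to 4 deal with a preferred term that recurs, and all three set the span as the whole study:

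- Rule 2: "A subject having experienced the same event (AE preferred term) more than once during the study will be counted only once".
- Rule 3, where severity or seriousness differs: "it will be counted only once with the worst grade and seriousness respectively".
- Rule 4, where causality differs: "it will be counted only once by considering the most-related documented degree of relationship".

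The tables these rules feed are laid out by treatment. SAP 6.3.3 states that "The incidence of TEAEs will be presented by treatment" and places each event by onset. An event that "occurs after the first dose up until right before the second dose, the AE(s) will be assigned to the first treatment"; for later events, "If the AE(s) onset date-time or date occurs after the second dose, the AE(s) will be assigned to the second treatment".

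SAP 8.4.1 also summarizes TEAEs by treatment and adds that "for each SOC and PT, subjects are only counted once". It takes the highest severity or relationship when an event recurs. It names neither the study nor the treatment as the span.

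SAP 3.1 gives both treatments to each group. Protocol 9.7.1 counts 20 subjects exposed to bexagliflozin alone and 20 exposed to the combination.

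**The concern.** One count per subject and preferred term over the study suits a parallel-group trial, where a subject belongs to one column. Here each subject belongs to two. If someone has nausea in both periods, the onset rule produces two records, one per treatment, and each column needs one count. Rule 2 as worded allows one in total.

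The severity and causality rules add a second problem that remains even if subjects are counted within treatment. If the worst grade and closest relationship are still sought over the whole study, a mild, unrelated event on bexagliflozin alone could appear in that column with the severity or causality recorded under the combination. Protocol 9.7.1 calls for TEAE tabulations by severity and relationship, and SAP 8.4.1 plans a table of serious TEAEs by treatment, so this reaches planned output.

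The secondary objective is the safety and tolerability of bexagliflozin given with exenatide, and the by-treatment TEAE tables are its main adverse event summary.

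**Working it through.** **Inputs.** From the documents: 20 subjects exposed to each treatment (protocol 9.7.1), so one subject is 1/20 = 5 percentage points; counting span of the whole study (SAP 6.3.3.4, rules 2 to 4); tables by treatment (SAP 6.3.3, 8.4.1). The documents give no adverse event rates, so every rate and overlap below is assumed. There is no planned figure to reproduce.

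**Formula.** For one preferred term, let *a* be the subjects with it on bexagliflozin alone, *b* on the combination and *d* under both.

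- Counted within treatment: *a*/20 and *b*/20, together *a* + *b* counts.
- Counted once per study: *a* + *b* − *d* counts over the two columns.
- Counts lost: *d*.

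**How large is *d*?** With rates p (alone) and q (combination), the expected *d* is 20·p·q if occurrences are independent within a subject. The maximum is 20·min(p, q).

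| Assumed rates (alone/combination) | Expected loss, independence | Maximum loss |
|---|---|---|
| 5% / 20% | 20 × 0.05 × 0.20 = 0.2 | 20 × 0.05 = 1 |
| 10% / 30% | 20 × 0.10 × 0.30 = 0.6 | 20 × 0.10 = 2 |
| 20% / 40% | 20 × 0.20 × 0.40 = 1.6 | 20 × 0.20 = 4 |
| 30% / 50% | 20 × 0.30 × 0.50 = 3.0 | 20 × 0.30 = 6 |

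If the same subjects tend to repeat an event, the loss lies above the independence figure.

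**Effect on the contrast.** Assume *a* = 4, *b* = 8, *d* = 3.

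- Within treatment: 4/20 = 20% against 8/20 = 40%; difference 20 points.
- Once per study, repeats removed from the alone column: (4 − 3)/20 = 5% against 40%; difference 35 points.
- Once per study, repeats removed from the combination column: 20% against (8 − 3)/20 = 25%; difference 5 points.
- Once per study, first-period record kept, with repeats split evenly between the two sequences: (4 − 1.5)/20 = 12.5% against (8 − 1.5)/20 = 32.5%; difference still 20 points, but both incidences are too low.

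**Which record is kept?** The SAP does not say. If rule 3 is taken to place the count with the worse grade and rule 4 with the closer relationship, the two can point to different treatments for the same subject and term.

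**The case against.** The strongest reply is that the SAP, read as a whole, already implies the right count. SAP 6.3.3 assigns each event to a treatment by onset. SAP 8.4.1 speaks of summaries by treatment before it says subjects are counted once per class and term, and it does not mention the study as the span. A programmer would probably count once per subject within each column. A once-per-study count could not even be programmed into two columns without a rule for which treatment keeps a shared event, and there is none. The table shells, held in a companion document, may settle the matter.

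Much of this stands. A reader might infer that a subject with the same event under both treatments is dropped from one column as a settled matter, or that SAP 8.4.1 repeats the study-wide rule. The documents support neither reading: the loss can occur, and SAP 8.4.1 leans towards the within-treatment count.

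The reply does not remove the point. The onset rule says where an event belongs; the counting rule says how often the subject counts, and rules 2 to 4 state the study as the span three times. A rule that gives the right table only when its wording is set aside needs correcting. Nor does the reply answer the carry-over of severity and causality.

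Two limits are also fair. If no subject has the same term under both treatments, nothing changes. And since all events are listed, by-treatment counts could be rebuilt from the listings.

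**Conclusion.** The concern holds as a wrong scope in a stated rule, and the SAP is ambiguous as a result. Taken literally, rules 2 to 4 let a subject with a shared preferred term count under only one treatment, without saying which. Under a within-treatment count, rules 3 and 4 can still misplace severity, seriousness or causality.

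The size depends on assumptions. For the assumed rates, the expected loss per preferred term is about 0.2 to 3.0 subjects under independence, and at most 1 to 6. No direction of bias in the treatment contrast can be claimed: it depends on which record is kept, and keeping the first-period record leaves the difference unchanged on average.

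A reader might also infer that the secondary objective is a formal safety comparison with bexagliflozin alone. It is not. The objective (protocol 2.2, SAP 2.2) names only the combination, and SAP 3.3 plans no hypothesis testing; the by-treatment tables allow a descriptive contrast. Only those descriptive safety tables are affected. The PK and PD analyses are untouched. The change should be made, but it does not threaten the trial's main conclusions.

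**What to change.** - In SAP 6.3.3.4, rules 2 to 4, replace *during the study* with *within the same treatment*.
- Add *within each treatment* to rule 1, and to the sentences of SAP 8.4.1 on counting by class and term and on highest severity and relationship. The study-wide phrase does not occur in those places, so this is an addition, not a replacement.
- Keep once-per-study counting only for an overall column, if one is shown.
- Check that the companion table shells agree.

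The cost is SAP wording. Programming effort is the same, and no data collection or design element changes. SAP section 10 already provides for a documented revision before database lock.

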6.3.3.5 AE Severity

Adverse events will be graded on a 3-point scale and reported as indicated on the case report form (CRF). The intensity of an adverse experience will be graded as “Mild”, “Moderate”, and “Severe” using the criteria specified in Section 6.9 of the study protocol.

6.3.3.6 Relationship to the Investigational Medicinal Product

The relationship of an AE to dosing will be assessed as “Definite”, “Probable”, “Possible”, “Not Likely”, or Unrelated using the criteria specified in Section 6.9 of the study protocol.

6.3.3.7 AE with Irregular Start/End Dates

Partial dates may be imputed when appropriate. Imputed dates will be used to determine Study Day.

If a partial date is reported for the start of an AE, a complete date will be imputed by the following algorithm:

1. Only the year is reported: If the subject started receiving study medication in the previous year, then January 1 will be used as the starting date of the event. If the subject started receiving study medication in the year reported, then the date of the first dose of study medication will be used as the start of the event.
2. The month and year is reported: If the subject started receiving study medication prior to the month and year reported, then the first day of the month will be used as the starting date of the event. If the subject started receiving study medication during the month and year reported, then the date of the first dose of study medication will be used as the start of the event.

If a partial date is reported for the end of an adverse event and the adverse event is not continuing, a complete date will be imputed by the following algorithm:

1. Only the year is reported: If the subject started receiving study drug in the previous year, then the date of final study contact with the subject will be used as the end of the adverse event. If the subject started receiving study medication in the year reported, then the earlier of December 31 or the date of final study contact with the subject will be used as the end of the adverse event.
2. The month and year is reported: The earlier of the last date of the month or the date of final contact with the subject will be used as the end of the AE.

The above rules are subject to logical sense, for example, imputed start date should be on or prior to imputed end date.

All AEs will be included in the listings regardless the completeness of the onset dates.

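### SAP 6.3.3.7 imputes partial AE start dates without looking at the Day 8 dose, so most partially dated Period 2 AEs count under the Period 1 treatment, and no rule assigns a treatment to a worsening

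*SAP*

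**What the plan says.** **Partial start dates (SAP 6.3.3.7).**
- Month and year known, dosing began in that month: the start becomes the first dose date. The rule applies if dosing began "during the month and year reported, then the date of the first dose of study medication will be used as the start of the event".
- Month and year known, dosing began in an earlier month: "then the first day of the month will be used as the starting date of the event".
- Year only: the first dose date if dosing began that year. If it began the year before, "then January 1 will be used as the starting date of the event".
- Status of the rules: "Partial dates may be imputed when appropriate", and "Imputed dates will be used to determine Study Day". The closing safeguard is: "The above rules are subject to logical sense, for example, imputed start date should be on or prior to imputed end date".

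**Treatment assignment (SAP 6.3.3).** If the "onset date-time or date occurs after the first dose up until right before the second dose, the AE(s) will be assigned to the first treatment". Onset after the second dose goes to the second treatment. Protocol 9.7.1 works the same way.

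**Worsening (SAP 6.3.3.1).** The definition of treatment-emergent also covers an AE that starts earlier "or worsens during the treatment period (intensity/severity grades worsen". Neither SAP 6.3.3 nor 6.3.3.1 says which treatment the worsening counts under.

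**Use.** SAP 8.4.1 tabulates treatment-emergent AEs by treatment. These tables serve the secondary objective (SAP 2.2), the safety and tolerability of the combination.

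**The concern.** The imputation rule suits a parallel-group trial, where anything after the first dose belongs to one treatment. Here each subject is dosed on Day 1 and again on Day 8 with the other treatment. The two doses usually share a calendar month and nearly always a year. Imputing to the first dose therefore moves a Period 2 onset back to Day 1, and assignment by onset then places it under the wrong treatment. In Group 1, events on the combination move to bexagliflozin alone. In Group 2, events on bexagliflozin alone move to the combination.

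Assignment by onset also leaves a gap for worsening. An AE can enter the tables because it worsened after a dose, yet be placed by an onset that came before that dose.

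A treatment contrast is plausible: Protocol 1.2 names gastrointestinal events as the most common with this drug class. With 20 subjects, a few moved events can change a row of the table. Elsewhere the SAP does respect periods; SAP 6.3.5 and 6.3.6 define vital-sign and ECG baselines within each one.

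**Working it through.** The documents give no AE rate and no count of partial dates, so there is no plan figure to reproduce. The rates below are assumptions.

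**1. Where a partially dated Period 2 event lands.** Inputs: Day 8 = Day 1 + 7 (Protocol Table 1; SAP Table 1), the SAP 6.3.3.7 start-date rules and the SAP 6.3.3 assignment rule. Assumptions: every Day 1 date in 2017 equally likely, and true onset on Day 8, 9 or 10. That gives 365 × 3 = 1,095 cases.

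For month-and-year dates the exceptions can be counted by hand:
- Day 8 is the last day of a month: onset on Day 9 or 10 is imputed to the 1st of the next month, after Day 8 (2 cases).
- Day 8 is the second-last day of a month: the same for onset on Day 10 (1 case). Over 12 month-ends, 3 × 12 = 36 cases go correctly to Period 2.
- Day 8 is the 1st of a month: all three onsets are imputed to the Day 8 date itself, which cannot be placed without a time. Again 3 × 12 = 36 cases.
- All others go to Period 1: 1,095 - 36 - 36 = 1,023.

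| Start date reported | To Period 1 (wrong) | To Period 2 | On Day 8 date |
|---|---|---|---|
| Month and year | 1,023 (93.4%) | 36 (3.3%) | 36 (3.3%) |
| Year only | 1,089 (99.5%) | 3 (0.3%) | 3 (0.3%) |

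Examples:
- Day 1 on 5 June, onset 13 June, reported as June: imputed to 5 June, Period 1, wrong.
- Day 1 on 28 June, Day 8 on 5 July, onset 6 July, reported as July: imputed to 1 July, Period 1, wrong.
- Day 1 on 22 June, Day 8 on 29 June, onset 1 July, reported as July: imputed to 1 July, Period 2, right.

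With onset on Days 8 to 12 (SAP 6.1.1 lets the Day 10 visit window run to Day 12), the Period 1 shares are 1,645/1,825 = 90.1% and 1,810/1,825 = 99.2%.

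True onsets on Days 1 to 7 go to Period 1 in all 2,555 of 2,555 cases, which is correct.

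**2. Effect on the treatment contrast.** Take 10 subjects per sequence, event rate *a* on bexagliflozin alone and *b* on the combination, and a share *q* of Period 2 events misassigned, equal in both sequences. Expected event counts are:
- alone = 10a + 10a(1 - q) + 10bq
- combination = 10b + 10b(1 - q) + 10aq
- difference = 20(b - a)(1 - q)

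The fraction retained is (1 - q), whatever *a* and *b* are. With assumed a = 10% and b = 30%:

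| q | Alone | Combination | Difference retained |
|---|---|---|---|
| 0 | 2.0 | 6.0 | 100% |
| 5% | 2.1 | 5.9 | 95% |
| 20% | 2.4 | 5.6 | 80% |
| 100% | 4.0 | 4.0 | 0% |

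*q* is a share of Period 2 events, not of all events. If 20% of Period 2 events had month-and-year dates only, q would be about 0.20 × 0.934 = 18.7%.

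**3. Worsening.** Consider only AEs with onset in Period 1 that worsen after the Day 8 dose, and assume the worsening stays on the original record. If this happens in 10% of the 10 subjects then on bexagliflozin alone and 30% of the 10 then on the combination, the true counts are 1 v 3. Assignment by onset gives 3 v 1, so within this subset the contrast is reversed. An AE with onset before Day 1 that worsens after dosing is treatment-emergent but fits neither assignment rule.

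**The case against.** **Exposure is small.** Subjects are confined on Days 0 to 3 and 7 to 10 with AEs collected throughout (Protocol 3.1, Appendix 1), so most Period 2 onsets should be fully dated. Vague dates are likeliest at home between Days 3 and 7, and the current rule gets those right. This stands and limits the size. Partial dates are also plausible for events after Day 10 discharge, however, and those belong to Period 2.

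**The rules are discretionary.** Imputation is optional, its stated purpose is Study Day, and common sense may override it. An analyst who knows that an event was recorded after the Day 8 dose is not clearly bound to date it Day 1. This stands in part, since use of the imputed date for treatment assignment is inferred. But if the imputed date is not used, the SAP has no stated way to assign a partially dated event that could belong to either period. The one example of a sense check, start no later than end, can never catch a start moved too early.

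**Safety is descriptive.** SAP 3.3 plans no hypothesis test, and every AE is listed however incomplete its date. That lowers the stakes, but the comparison is still read from the by-treatment tables.

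**Stronger readings the documents do not support.**
- A reader might infer that every partial start date goes to Period 1. The first-of-month and January 1 branches can land on or after Day 8, and true Period 1 events are placed correctly.
- A reader might infer that every AE worsening after the Day 8 dose goes to Period 1. An AE that began after that dose goes to the second treatment, and one that began before Day 1 goes to neither.
- A reader might infer that a worsened AE is charged to Period 1 at its worst grade. The worst-grade rules in SAP 6.3.3.4 and 8.4.1 concern repeat occurrences, not one continuing AE. The documents do not say whether a worsening opens a new CRF record with its own onset; if it does, SAP 6.3.3 assigns it correctly.

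**Conclusion.** Wrong as written, minor in size. Under the stated rules, a Period 2 AE with a partial start date is usually counted under the Period 1 treatment, and for the misassigned events the expected treatment contrast is lost. Overall, (1 - q) of the difference remains. The percentages rest on equally likely Day 1 dates in an assumed year, onset on Days 8 to 10, and use of the imputed date for assignment. The (1 - q) result rests on equal group sizes and the same *q* in both sequences. The documents do not give *q*; in-clinic observation suggests that it is low.

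The worsening gap is real but conditional. It misplaces Period 1 onsets only if a worsening is kept on the original record, and on that same condition leaves pre-Day 1 onsets unassigned. It arises from assignment by onset in SAP 6.3.3 and the absence of a rule for worsening, not from the treatment-emergent definition itself.

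**What to change.** **SAP 6.3.3.7.** Where a partial start date is compatible with both periods, set the period by whether the AE was first recorded, or ended, before or after the Day 8 dose:
- First recorded or ended before that dose, including at Day 7 or Day 8 pre-dose: assign to the first treatment and keep the current imputation.
- First recorded after that dose, with nothing showing earlier onset: assign to the second treatment and impute the Day 8 dose date.
- Period cannot be determined: list the event and show it under each treatment in a sensitivity table.

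Do not use the visit label for this. Day 7 is a Period 2 visit but precedes the second dose, so an event that arose at home on Days 3 to 7 and was first reported on Day 7 would move to the wrong treatment.

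**SAP 6.3.3.** Assign an AE that is treatment-emergent by worsening to the treatment most recently given before the worsening, at the worsened grade. Any Period 1 onset stays counted under the first treatment at its Period 1 grade.

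**Cost.** A few sentences in two SAP sections and a small programming change. The sensitivity table is needed only if undetermined cases occur.
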